confirmatory synchronous screening by phone. The invitation to complete the baseline assessment is sent to participants after eligibility confirmation via text message. After baseline is complete, participants are invited to complete an installation session wherein they are introduced to their intervention, and oriented to study details. Participants are randomized to condition (via a pre-set stratified randomization algorithm, see above) at the time of the installation session.

Once participants have installed and been oriented to their study app, members of the study team are available to answer questions about study interventions or respond to concerns about the study. Up to three times during the study period, participants receive outreach via text message and phone call if they stopped using the app for five consecutive days (confirmed via app usage logs). This outreach assesses for technical issues or concerns from participants about app use. Subsequent assessments are sent to participants via text messages 6 and 12 weeks after they installed the NORTH app, and participants are also invited to complete weekly questionnaires to report actual treatment engagement frequency. Participants are compensated with \$60 gift cards for completing each assessment battery (or, in the case of baseline, baseline and installation session both).

Interventions. NORTH (Normalizing ORientation to Treatment and Help-Seeking) is a self-guided iOS mobile app designed to provide self-guided coping support to individuals experiencing early psychosis. It combines video, audio, and written text, and draws on principles of cognitive behavior therapy and motivational enhancement. While both NORTH “full” and NORTH “lite” contain lessons (i.e. introductory modules to new skills), practices (i.e. opportunities to practice skills through video coaching or written prompts), and tracking (i.e. rating changes in a well-being score over time), only participants with NORTH “full” receive in-app treatment-seeking and psychoeducational content. Note that all participants regardless of condition receive thorough materials about mental health symptoms, treatment options, and crisis resources. For participants in the NORTH “full” condition, treatment-seeking and in-depth psychoeducation is a focus of interactive mHealth content, whereas in the “lite” arm, only the self-management components can be found in-app.

Outcome Measures. Primary and secondary registered measures are listed below.

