Modified Usability Scale	Intervention Acceptability / Usability	Usability/Acceptability will be assessed with a modified version of the System Usability Scale derived from our group's previous work developing mHealth interventions. This composite measure, which comprises 26 items based on four measures - the System Usability Scale, Post Study System Usability Scale, Technology Assessment Model Measurement Scales, and Usefulness, Satisfaction and Ease Questionnaire - assesses participants' experiences with the intervention during the study period (1 = Disagree, 2 = Neutral, 3 = Agree). While this measure is often interpreted qualitatively by item, we will also compare the overall score, which will comprise an average and thus range from 1 to 3, with higher scores reflecting higher acceptability and usability.	6 weeks

DATA ANALYTIC PLAN

Clinical-trial data analyses. Linear regression will be used for continuous outcomes wherein participant and treatment condition are clustered as independent variables (i.e. adjusting for the baseline value of the outcome measure relevant to each model). We will separately model outcomes at 6 weeks and 12 weeks respectively. Within-condition changes will also be modeled using linear regression with assessment and value at baseline as independent variables. Effect sizes will be estimated using Cohen's d and 95% confidence intervals. Mean imputation is used to generate total scale scores consistent with measure convention (i.e. totaling sums or means) in instances when participants complete fewer than 50% of scale items. Descriptive outcome measures (i.e. measures of usability and acceptability) will be described qualitatively as well as compared with independent-samples t-tests. As this is a pilot trial with limited statistical power, we will model and interpret direction and size of effects for primary outcomes.

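### With separate 6- and 12-week regressions and no rule for a wholly missed assessment, the 12-week comparison is by natural reading complete-case; one two-visit model would use the 6-week scores it discards, at little cost.

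*Combined protocol and SAP*

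**What the plan says.** All of the analysis text is in the combined protocol and SAP, Data Analytic Plan, under Clinical-trial data analyses. Continuous outcomes are analysed by linear regression adjusted for the baseline value of the outcome. On the two follow-ups it says: "We will separately model outcomes at 6 weeks and 12 weeks respectively". It adds that "participant and treatment condition are clustered as independent variables".

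The one sentence on missing data begins "Mean imputation is used to generate total scale scores consistent with measure convention" and concerns building a scale total when some items are unanswered. There is no rule for a missed assessment, no definition of the analysis set, no expected attrition and no missing-data sensitivity analysis.

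On inference the plan says that "we will model and interpret direction and size of effects for primary outcomes".

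The outcome measures table schedules every scale at baseline, 6 weeks and 12 weeks, except usability, which is collected at 6 weeks only. The Procedures section has follow-up assessments sent by text message.

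**The concern.** An ordinary regression on the 12-week score needs that score, so anyone who answered at 6 weeks and not at 12 leaves the 12-week model. If such people were doing better or worse than others at 6 weeks, and this pattern or the amount of dropout differs between arms, the remaining participants no longer give a fair comparison at 12 weeks.

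A difference between arms is conceivable because only the full version carries treatment-seeking content in the app. The documents neither show nor exclude it.

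The plan draws its conclusions from the direction and size of effects, so a shift in the estimate passes straight into the reading of the trial. The 6-week scores that could correct much of this are already scheduled.

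**Working it through.** The plan states no attrition rate, correlation or power calculation, so there is no figure of its own to reproduce.

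**Inputs from the documents.** 60 participants randomized 1:1 (30 per arm); scores at baseline, 6 and 12 weeks.

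**Assumptions, none from the documents.** Correlations 0.6 (baseline with 6 weeks), 0.7 (6 with 12 weeks) and 0.5 (baseline with 12 weeks). Missing at 6/12 weeks: 10%/20% to 15%/30%. Missingness at 6 weeks is random, and those people are also missing at 12. Later dropout has log-odds slope 1 per SD of the 6-week score. There is no true effect unless stated.

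**1. Who is discarded.** At 10%/20%, 54 people have a 6-week score and 48 a 12-week score, so 6 are lost. At 15%/30%, 51 − 42 = 9 are lost.

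**2. Bias by formula.** Let c = r(6,12) − r(b,6) × r(b,12) = 0.7 − 0.6 × 0.5 = 0.40, the covariance of the 6- and 12-week scores after removing baseline. Let q be the dropout rate after week 6 among those seen at week 6, and K the average of p(1 − p) over the 6-week score, where p is the logistic dropout probability. In an arm with slope s, the baseline-adjusted 12-week mean of those retained shifts by about c × s × K/(1 − q) in size.

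- 10%/20%: q = 0.10/0.90 = 0.111; K = 0.089; shift = 0.40 × 0.089/0.889 = 0.040 SD.
- 15%/30%: q = 0.15/0.85 = 0.176; K = 0.127; shift = 0.40 × 0.127/0.824 = 0.062 SD.
- One arm affected: 0.04 to 0.06 SD. Opposite directions: twice that, 0.08 to 0.12 SD.
- Same dependence, 15% v 25% missing at 12 weeks: K/(1 − q) = 0.052 v 0.146; 0.40 × 0.094 = 0.038 SD. For 25% v 35%: 0.106 v 0.202; 0.40 × 0.096 = 0.038 SD.
- Same dependence, equal rates, no true effect: the shifts cancel. Random dropout: s = 0. Dropout on baseline alone: the baseline adjustment absorbs it.

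**3. Simulation check** (1.5 million per arm). Complete-case regression against the joint two-visit estimate; absolute bias in SD:

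| Dropout after week 6 | Complete-case | Two-visit |
|---|---|---|
| Depends on 6-week score, one arm | 0.04–0.06 | about 0.00 |
| Depends on it, opposite directions | 0.08–0.13 | about 0.00 |
| Same dependence, rates 10 points apart | 0.04 | about 0.00 |
| Same dependence, equal rates | 0.00 | 0.00 |
| Random, or on baseline alone | 0.00 | 0.00 |

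**4. Dependence on the correlations** (15%/30% missing), where K/(1 − q) = 0.154 and c changes. Correlations are listed as baseline–6, 6–12, baseline–12:

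| Correlations | c | One arm | Opposite |
|---|---|---|---|
| 0.6, 0.7, 0.5 | 0.40 | 0.06 | 0.13 |
| 0.6, 0.6, 0.5 | 0.30 | 0.05 | 0.09–0.10 |
| 0.6, 0.8, 0.5 | 0.50 | 0.08 | 0.16 |
| 0.7, 0.6, 0.6 | 0.18 | 0.03 | 0.06 |
| 0.5, 0.8, 0.4 | 0.60 | 0.09–0.10 | 0.19 |

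Moving all three together by 0.1 leaves c at 0.40 or 0.38 and hardly changes the bias. Varied separately, the range is 0.03 to 0.10 SD (one arm) and 0.06 to 0.19 SD (opposite).

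**5. Scale.** In simulated trials of 30 per arm the 12-week estimate has SD about 0.25 to 0.27. With a true effect of 0.3 SD and bias against it, the complete-case estimate has the wrong sign in about 15% to 19% of trials (one arm) or 20% to 26% (opposite), against 12% to 13% for the two-visit model.

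The precision gain is small. The variance ratio is 1 − r²(1 − n12/n6), with r² = 0.40²/(0.64 × 0.75) = 0.333. This gives 1 − 0.333 × (1 − 48/54) = 0.963 and 1 − 0.333 × (1 − 42/51) = 0.941, so the confidence interval is about 2% to 3% narrower.

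**6. Limit of the remedy.** If dropout depends on the 12-week score itself, the complete-case bias is 0.08 to 0.12 SD (one arm) or 0.15 to 0.24 SD (opposite). The two-visit model still leaves 0.05 to 0.08 or 0.10 to 0.16 SD, about two thirds.

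**The case against.** The strongest reply is one of proportion. This is a pilot with admittedly limited power. Every dropout input above is assumed, and in the one-arm case root-mean-square error falls only about 2% to 5% with the joint model. Nothing in the documents suggests the opposite-direction pattern that gives the larger figures. All of that stands, and it makes this an inexpensive improvement, not a defect that undermines the trial.

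The conduct of the trial may also hold losses down. The Procedures section provides "gift cards for completing each assessment battery", and says: "Up to three times during the study period, participants receive outreach via text message and phone call if they stopped using the app". It also says: "Participants are randomized to condition (via a pre-set stratified randomization algorithm, see above) at the time of the installation session". The last means that people who never reach the installation session are not counted as losses after randomization. These measures may reduce missing assessments. They do not say how those that remain will be analysed.

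Two textual escapes do not work. The wording on clustering by participant might hint at a repeated-measures model, but a separate model for each visit has one row per person, so it cannot borrow from the other visit. The item rule, read literally, covers someone who completed no items, but it is about forming scale totals, and a person's mean cannot be formed from no answers. The within-condition models give no between-arm contrast.

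A reader might infer that separate models are invalid, or that unequal dropout alone biases the result. Neither follows: unequal rates of random dropout give no bias.

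**Conclusion.** The point holds as a modest, conditional weakness. The plan gives no rule for a missed assessment, and by natural reading its 12-week comparison discards known 6-week scores. The estimate is biased only if dropout depends on the 6-week score and that dependence or the dropout rate differs by arm. Under the stated assumptions the bias is about 0.04 to 0.06 SD (one arm), 0.08 to 0.13 SD (opposite directions) or 0.04 SD (rates 10 points apart).

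These figures are not robust to the assumed correlations: separate changes of 0.1 can roughly halve them or raise them by half. Even the larger values are below the sampling error of a 60-person trial.

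A reader might go further and infer that the 12-week result will be biased, or that much precision is lost. The documents report no dropout rate or mechanism, so the first cannot be claimed, and the arithmetic contradicts the second. Nor does the two-visit model cure everything: it assumes data are missing at random given observed scores, and it cannot recover people who miss both follow-ups.

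**What to change.** For each outcome scheduled at both follow-ups:

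- Make the between-arm analysis one likelihood-based repeated-measures model of the 6- and 12-week scores, with condition, visit, condition × visit, baseline, baseline × visit and unstructured covariance.
- Report the condition effect with its 95% confidence interval at each visit, so the plan still gives separate 6- and 12-week results.
- Report the number missing by arm and visit.
- Keep the planned separate regressions as a sensitivity analysis.

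For the primary outcomes, add a simple delta-shift analysis: move the implied 12-week values of those missing, one arm at a time, for example by up to ±0.5 SD. The effect moves by the proportion missing times the shift, 0.20 × 0.5 = 0.10 SD or 0.30 × 0.5 = 0.15 SD. This addresses dropout that depends on the 12-week score itself.

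Usability, collected at 6 weeks only, is unaffected. The weekly questionnaires are not needed for this change: participants are only invited to complete them, and the documents give no link between those reports and the outcome scales.

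The cost is SAP wording, some extra programming across several scales and an explicit missing-at-random assumption. No new data are needed, and with complete data the per-visit estimates would be essentially unchanged. The change should be fixed before outcome data by arm are examined.

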Design. This is a parallel group randomized controlled trial design. Participants are randomized 1:1 to either NORTH “lite” or NORTH “full.” Randomization is stratified based on whether the individual had engaged in mental health treatment (per inclusion criterion i.e. either regular psychotherapy or antipsychotic medication) within the past year vs. longer than one year ago (or not at all). Primary outcome assessments are collected at (1) baseline, (2) 6 weeks after app installation, and (3) 12 weeks after app installation.

METHODS

Participants. Participants are 60 treatment-unengaged young adults experiencing psychosis symptoms indicating need for evaluation and/or treatment who meet the following criteria: (1) age 18-30, (2) living in the US, (3) owning an iPhone, (4) symptoms of psychosis as measured by both (4a) a score ≥ 20 on the Prodromal Questionnaire, Brief (PQB), (4b) a positive frequency average score ≥ 1.47 on the Community Assessment of Psychic Experiences (CAPE-P15), and (4c) a score ≤ 8 on the Moritz CAPE lie scale designed for online data collection, (5) less than five years since a first episode of psychosis or awareness of symptom onset, and (6) unengaged in specialty mental health services in the previous three months as defined either (6a) having taken a prescribed antipsychotic medication, (6b) or having attended regular psychotherapy. Exclusion criteria included (1) failure to accurately complete consent comprehension questions or (2) being unengaged in mental health services because of having completed or “graduated” from a specialty mental health program.

Recruitment. Participants are recruited through online study ads (i.e. Google, Instagram, and YouTube) as well as distribution through mental health advocacy organization and treatment websites and listservs.

Procedures. All screeners and study questionnaires are completed through online data capture (i.e. REDCap). Once participants click a link to the study landing page from a recruitment ad or posting, they are required to demonstrate understanding of study details through a comprehension questionnaire, provide informed consent and are subject to a series of steps to ensure eligibility for the study and identity verification. Study team members evaluate screening data and conduct

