Measure	Construct	Description	Time Frame
Measure to Assess Steps to Service (MASS)	Change in Treatment Seeking Steps	Treatment seeking will be measured using the Measure to Assess Steps to Service (MASS). The MASS is a 17-item self-report assessment of steps taken towards the attainment of mental health treatment, including research, social support, and engagement with service provider steps. Each item is endorsed on a three-point Likert scale (0 = No, I have not done this, 1 = I have done this once or twice, 2 = I have done this multiple times). The MASS is scored by summing individual items with higher scores indicating greater levels of treatment-seeking actions.	Baseline, 6 weeks, 12 weeks
Endorsed and Anticipated Stigma Inventory (EASI) – Beliefs about Treatment / Beliefs about Treatment-Seeking subscales	Change in Treatment-related Attitudes / Beliefs	Help-Seeking Attitudes and Stigma will be measured primarily using the Endorsed and Anticipated Stigma Inventory (EASI). The full EASI is a 40-item self-reported questionnaire with subscales measuring beliefs about mental illness, beliefs about mental health treatment, beliefs about mental health treatment seeking,	Baseline, 6 weeks, 12 weeks

		
concerns about stigma from loved ones, and concerns about stigma from the workplace. The subscales are scored by summing the ratings from the eight individual items in each subscale (5-point scale with 1 = Strongly disagree, 5 = Strongly agree), with lower scores indicating less stigma, and more positive attitudes towards treatment and treatment-seeking.
 
The Beliefs About Treatment scale assesses individuals' beliefs about the efficacy and usefulness of mental health treatments. It is totaled as a sum, with higher scores indicating more stigmatizing attitudes toward treatment.
 
The Beliefs About Treatment Seeking scale assesses individuals' attitudes toward seeking mental health treatments. It is totaled as a sum, with higher scores indicating more stigmatizing attitudes toward treatment seeking.
	

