Internalized Stigma of Mental Illness Inventory (ISMI-9)	Change in Internalized Stigma	The Internalized Stigma of Mental Health Inventory, Brief (ISMI-9) will provide additional insight into the strength of participants' internalized stigma of mental illness. The ISMI-9 is a nine-item self-report short form, where each item is rated on a four-point Likert scale (1 = Strongly disagree, 4 = Strongly agree) and totaled as a mean score. Thus scores range from 1 to 4 with higher scores indicating more severe internalization of mental illness stigma.	Baseline, 6 weeks, 12 weeks
Perceived Stress Questionnaire (PSQ)	Change in Perceived Stress	Perceived stress will be measured using the Perceived Stress Questionnaire (PSQ), which is a 30-item, self-report questionnaire that examines the experience of stress independent of a specific and objective occasion. Items are endorsed on a four-point scale (1 = Almost never, 4 = Usually), and are summed for a total score (ranging from 30 to 120), with higher scores indicating higher levels of perceived stress.	Baseline, 6 weeks, 12 weeks
Brief Resilience Scale (BRS)	Change in Resilience / Coping	The Brief Resilience Scale (BRS) will be used to assess resiliency. The BRS is a self-report form that consists of six resiliency statements that participants agree or disagree with on a five-point scale (1 = Strongly disagree, 5 = Strongly agree). Scores are totaled as a mean, and thus range from 1 to 5, with higher scores indicating greater resilience.	Baseline, 6 weeks, 12 weeks

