Community Assessment of Psychic Experiences	Change in Symptoms	
The Community Assessment of Psychic Experiences (CAPE-42) will be used to assess positive, negative and depressive symptoms of psychosis. The CAPE-42 is a self-report, 42 two-part item assessment that measures both the frequency of experiencing symptoms (four-point scale, 1 = Never, 4 = Almost Always) as well as the distress level (four-point scale, 1 = Not Distressed, 4 = Very Distressed) associated with each endorsed symptom. The CAPE weighted score can be calculated by summing the frequency and distress item responses.
 
The positive subscale is 20 items and is totaled as a mean response ranging from 2 to 8, with higher scores indicating more frequent and distressing positive symptoms.
 
The negative subscale is 14 items and is totaled as a mean response ranging from 2 to 8, with higher scores indicating more frequent and distressing negative symptoms.
 
The depressive subscale is 8 items and is totaled as a mean response ranging from 2 to 8, with higher scores indicating more frequent and distressing depressive symptoms.
	Baseline, 6 weeks, 12 weeks
Choice of Outcome in CBT for Psychoses, Short-Form (CHOICE-SF)	Change in Recovery	
Recovery will be assessed using the Choice of Outcome in CBT for Psychoses, Short Form (CHOICE-SF). The CHOICE-SF is an 11-item self-report form developed to assess recovery-related goals for therapy. Participants rate themselves in different therapy-focused areas such as "self-confidence" or "ways of dealing with everyday stress" on a scale (0 = Worst, 10 = Best). Scores on the CHOICE-SF are totaled as mean score across all standard items, and thus range from 0 to 10 with higher scores reflecting improved recovery.
	Baseline, 6 weeks, 12 weeks
Sheehan Disability Scale	Change in Functioning	
Functioning will be measured using the Sheehan Disability Scale (SDS). The SDS is a short, five-item self-report form that assesses disability and functional impairment. The total score is the sum of three items measure to what extent symptoms have disrupted different aspects of daily life on a scale (0 = Not at all, 10 = Severely), thus the scale ranges
	Baseline, 6 weeks, 12 weeks

		from 0 to 30 with higher scores indicating greater functional impairment.	

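### The missing-item rule, as written, imputes scale totals when under half the items are answered and gives no rule for forms that are 50–99% complete

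*Combined protocol and SAP*

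**What the plan says.** The rule is in the Data Analytic Plan, under Clinical-trial data analyses: "Mean imputation is used to generate total scale scores consistent with measure convention (i.e. totaling sums or means", and this applies "in instances when participants complete fewer than 50% of scale items". The part about measure convention tells the analyst whether a scale is a sum or a mean. It sets no threshold, and it does not say whether the imputed mean is the participant's own or the sample's.

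The Outcome Measures table gives item counts and scoring but no missing-item rule. Four measures are sums:
- MASS: "The MASS is scored by summing individual items with higher scores indicating greater levels of treatment-seeking actions"
- EASI: "The subscales are scored by summing the ratings from the eight individual items in each subscale"
- PSQ: items "are summed for a total score (ranging from 30 to 120"
- SDS: "The total score is the sum of three items"

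The ISMI-9, BRS, CAPE, CHOICE-SF and usability scores are means. On data collection, Procedures states "All screeners and study questionnaires are completed through online data capture" and names REDCap. It does not say whether respondents can skip items.

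**The concern.** Item-level mean imputation is defensible when most of a scale has been answered, because the answered items then carry most of the information in the total. This rule is triggered by the opposite condition. An analyst who follows it turns a form with one or two answers into an outcome score and has no instruction for a form with one item missing.

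Two things are at stake. First, near-empty forms become scores on the MASS and the two EASI belief subscales, which carry the trial's question about treatment seeking and treatment attitudes. With 60 participants, and a pilot to be read on the sign and magnitude of its effects, a few such totals can move an arm mean. Second, sums need a rule that means do not. A nearly complete MASS, EASI, PSQ or SDS form must be prorated, summed short or dropped, and the plan does not say which.

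**Working it through.** The plan states no figure that depends on this rule (no power calculation and no expected missingness), so there is nothing of its own to reproduce.

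**1. Which partial forms the rule covers.** Inputs are the item counts k in the Outcome Measures table. The trigger is answered items m < k/2; forms with k/2 ≤ m < k have no rule.

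| Scale | k | Score | Imputed as written (m) | No rule (m) |
|---|---|---|---|---|
| MASS | 17 | sum | 1–8 | 9–16 |
| EASI subscale | 8 | sum | 1–3 | 4–7 |
| PSQ | 30 | sum | 1–14 | 15–29 |
| SDS total | 3 scored | sum | 1 | 2 |
| ISMI-9 | 9 | mean | 1–4 | 5–8 |
| BRS | 6 | mean | 1–2 | 3–5 |
| CAPE positive | 20 | mean | 1–9 | 10–19 |
| CAPE negative | 14 | mean | 1–6 | 7–13 |
| CAPE depressive | 8 | mean | 1–3 | 4–7 |
| CHOICE-SF | 11 | mean | 1–5 | 6–10 |
| Usability | 26 | mean | 1–12 | 13–25 |

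A form with no answers (m = 0) also meets the literal condition. It has no person mean, so only a sample mean could fill it.

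**2. Reliability of the resulting totals.** Assumption, not in the documents: parallel items and full-scale alpha 0.85, range 0.80–0.90. Inter-item correlation r = alpha / (k − (k − 1) × alpha). Reliability of m items = m r / (1 + (m − 1) r).

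- EASI subscale: r = 0.85 / (8 − 7 × 0.85) = 0.85 / 2.05 = 0.415.
- MASS: r = 0.85 / (17 − 16 × 0.85) = 0.85 / 3.4 = 0.250.

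| Form | Rule as written | Reliability at alpha 0.85 | Over alpha 0.80–0.90 |
|---|---|---|---|
| EASI, 1–3 of 8 | imputed | 0.41–0.68 | 0.33–0.77 |
| EASI, 7 of 8 | none | 0.83 | 0.78–0.89 |
| MASS, 1–8 of 17 | imputed | 0.25–0.73 | 0.19–0.81 |
| MASS, 16 of 17 | none | 0.84 | 0.79–0.89 |

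With the direction reversed, the least complete eligible forms are EASI 4 of 8, at 4 × 0.4146 / (1 + 3 × 0.4146) = 0.74, and MASS 9 of 17, at 9 × 0.25 / (1 + 8 × 0.25) = 0.75. The gain comes from having a floor. There is no sharp break at 50%: MASS 8 of 17 gives 0.73.

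**3. What one sparse form can do.** Under person-mean imputation, a MASS form with one answered item (scored 0, 1 or 2) can only total 17 × 0, 17 × 1 or 17 × 2, that is 0, 17 or 34. If the full total would have been 17 and the form is scored 0 or 34, a 30-person arm mean (60 randomized 1:1) shifts by 17/30 = 0.57 points. This is an illustrative extreme.

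**4. What the gap can do.** These figures apply only if mostly complete forms are left unimputed, which the plan does not state.

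- Summed short: an EASI respondent who answers 3 throughout and misses one item scores 7 × 3 = 21 instead of 8 × 3 = 24.
- Dropped: with an assumed independent skip probability q per item, the share of assessments lost is 1 − (1 − q)^k.

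| q | EASI subscale | MASS | PSQ | SDS |
|---|---|---|---|---|
| 1% | 8% | 16% | 26% | 3% |
| 2% | 15% | 29% | 45% | 6% |

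Mean-scored measures are generally not under-scored, because the mean of the answered items equals the person-mean-imputed score.

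**The case against.** The strongest reply is that this is a one-word slip. Had the text said 'miss' for 'complete', the inversion and the missing floor would disappear, along with nearly all of the gap. That is plausible, but nothing in the document shows it. The sentence is complete, current text in a document that is both protocol and SAP, and an analyst who silently reverses it departs from the published plan.

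The size of the harm is also open to challenge, and much of this stands. Alpha, parallel items and the skip rates are all assumptions. Parallel items is a doubtful model for the MASS, which counts different kinds of help-seeking step. Low reliability adds noise and does not by itself bias the comparison between arms. No MASS standard deviation is given, so the 0.57-point shift cannot be put in context. The CAPE items have two parts, so a form with only one part answered needs a further rule even for a mean score. None of this changes what the sentence tells the analyst to do.

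Finally, the plan has no stated method for missing assessments, so sending forms under 50% there may seem to point to nothing. In practice, a missing score simply does not enter that time point's regression, which is workable.

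**Conclusion.** The concern holds. As written, imputation is triggered by low completion, no minimum is set, and forms that are 50–99% complete have no rule. The reading of the text is secure; that the rule is the reverse of what was meant is an inference.

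The practical consequence falls mainly on the MASS, EASI subscales, PSQ and SDS. Under the assumed alpha of 0.80–0.90, the totals the rule creates have reliability as low as 0.33 (EASI) or 0.19 (MASS), while the forms it leaves out would reach 0.78–0.89 and 0.79–0.89 with one item missing. The effect on the trial's estimates is unknown, because no item-missingness rate is given. It is near zero if REDCap requires every answer. The sentence should be corrected: it is an operative scoring threshold, and it is wrong as it stands.

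**What to change.** Replace the sentence with:

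> Person-mean imputation (the mean of that participant's answered items on that scale) is used when at least 50% of the scale's items are completed; when fewer than 50% are completed, the scale score is set to missing for that assessment and treated like any other missing assessment in the regressions.

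This keeps the plan's own 50% cut-off, sets a floor, covers nearly complete forms and settles which mean is used. The sponsor should confirm that this is the intended direction. It would also help to state whether the REDCap forms allow items to be skipped.

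The cost is one sentence in the analysis plan, with no change to design or data collection. The downside is small: forms with under half the items answered no longer contribute a score.
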